An overview of the pilot RCT and the randomization scheme is shown in the Figure below. After being consented, all HHAs will attend a virtual orientation session and virtual HF training course. Prior to the course, all HHAs will complete a baseline questionnaire (see attached survey document) and be randomized in a 1:1 ratio (T1). The training course will be conducted via Zoom and led by WCM investigators and VNS Health staff members. After taking the course, HHAs in both arms will take a short post-course questionnaire (to assess the two primary outcomes; knowledge and HF caregiving self-efficacy). HHAs randomized to the enhanced usual care arm will receive a just-in-time course refresher via their Care Connect app (self-driven educational content) prior to caring for their HF patient. HHAs randomized to the intervention will receive a just-in-time course refresher as well as an app training session from a Weill Cornell Medicine research assistant (overseen by [name] in computer science). HHAs in this arm will be encouraged to use the app when they have questions about their patient, want to access HF-related content, or need to communicate with the nurse. To reinforce their use of the use of the application chat features, they will receive "do not reply" text based notifications reminding them that the feature is there and can be used. Following the care of their first patient, HHAs in both arms will take a follow-up questionnaire. Each HHA will be involved in the study for 90 days. During that time, if the HHA is assigned to a new HF patient, they can continue participation although they will remain randomized to their original treatment arm to avoid contamination. De-identified data on HF patients cared for by the HHAs (demographics, clinical conditions, ED visits; 30-day/90-day readmissions; hospitalization; functional status; and quality of life) will be retrospectively collected by the VNS Health from intake/referral data and OASIS. HHAs will receive \$100 for participating; they will receive \$25 at trial start, \$25 following the completion of the heart failure training course and survey 2, \$25 following the 45-day (mid-study) interview, and \$25 following the final survey.

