Functional status	N/A	Activities of daily living, physical function	Follow-Up VNS Health administrative data
Hospitalization	N/A	A hospitalization to any hospital (for any reason) during the study period	Follow-Up VNS Health administrative data
Quality of Life	Cardiomyopathy Questionnaire (Kansas City) [KCCQ-12]	The Kansas City Cardiomyopathy Questionnaire (KCCQ-12) is a 12-item self-administered questionnaire adapted from the KCCQ, a 23-item self-administered questionnaire which independently evaluates patient's perceptions of their health status with particular focus on heart failure symptoms, impact on physical and social function, the disease's impacts on their quality of life (QOL) within a 2-week recall period.	Interview

Sample Selection/Data Sources: English and Spanish speaking HHAs assigned to care for adults admitted to home care with a primary diagnosis of HF during the study period will be eligible. According to our preliminary estimates, VNS Health HHAs care for 2,280 new HF cases per year, for an estimated 4,560 cases during the 2-year trial. HHAs with less than 1 year of job experience will be excluded. We expect 400 HHAs will need to be screened to reach the goal of 104. Additionally, 12 nurses will be recruited (convenience sampling) to participate in pilot RCT.

HHAs will be studied for 90-days. HHAs will be asked to complete an electronic survey 3 times during the study; first before the virtual orientation session at the time of recruitment (beginning

of the trial; prior to randomization); second after receiving the HF training course; and lastly at 90 days after the completion of the training course.

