
Baseline analyses: For each baseline characteristic in the questionnaire (see attached document), we will examine the distribution and outliers. We will test whether baseline characteristics are balanced between intervention arms using parametric or non-parametric bivariate tests as appropriate. All tests will be conducted at $\alpha=0.05$.

Outcome analyses: Feasibility measures (described above) will be characterized with descriptive statistics (frequencies and proportions) using STATA statistical software. To assess the acceptability of the intervention and trial among study participants, [name] will conduct a series of exit interviews with HHAs and nurses in the trial, as well as with VNS Health staff. The effect of the intervention among HHAs will be assessed for **two primary outcomes:** 1) HF knowledge; 2) HF caregiving self-efficacy and **two secondary outcomes:** 1) intention to leave and 2) job satisfaction (See above Table); alongside other specified outcomes of interest including communication practices (and preventable 911 calls). Finally, the effect of the intervention on two patient outcomes (emergency department [ED] visits; 30-day readmissions; functional status) will be assessed in exploratory analyses. To determine the effect of the intervention on the **primary outcomes**, we will compare HF knowledge and HF caregiving self-

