efficacy scores by trial arm using paired t-tests for normally distributed data or Wilcoxon signed rank test for non-parametric data. We will examine the effect of randomization on the change in scores, using mixed linear regression models. Mixed-effects included a fixed effects categorical variable for time point (baseline/post-course/90 day), an indicator for study arm (control/intervention), a study arm by timepoint interaction and subject-specific random intercept. Primary analyses will be conducted using intention-to-treat, when appropriate. We will examine HHA characteristics across trial arms and adjust for covariates that are imbalanced ($p < 0.10$). We will conduct the same analyses for the secondary outcomes (burnout and job satisfaction). For patient outcomes, we will perform exploratory analyses to determine the effect of the intervention on ED visit rates and hospitalization rates; and functional status, using Poisson mixed effects regression models to account for clustering of patients within HHAs. To measure what would have occurred with usual care (e.g. without enhanced usual care or the intervention), we will assess ED visit rates and 30-day readmission rates among HHAs 90 days before vs. 90 days after randomization, adjusting for clustering of patients within HHAs, and stratified by trial arm. Analyses will be done using STATA statistical software.

Power and Sample Size: To detect minimal clinically important differences (MCID) for both outcomes (a 1-point change in mean score on the Dutch HF Knowledge Scale; an 8-point change in mean score on the HF caregiving self-efficacy), with 80% power, α at 0.05, and conservatively allowing for 15% attrition, we will need 104 HHAs (52 per arm). The overall α at 0.05 enables testing of two hypotheses using Bonferroni's method. Consistent with the goals of this study (to assess feasibility and acceptability of the intervention and obtain preliminary effectiveness estimates on primary outcomes), we have not powered our study on secondary outcomes or on patient outcomes. These calculations were done in Stata v13, College Station, TX.

Statement of the Risks/Benefits for the Study Subjects:

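### Within-arm paired tests are assigned to measure the intervention effect, and the plan names neither a primary analysis nor a primary timepoint

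*Combined protocol and SAP*

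**What the plan says.** **Analysis.** In the combined protocol and SAP, under Brief Overview of Analytic Methods (Outcome analyses), the sentence that sets out how the intervention effect on the two primary outcomes will be determined reads "we will compare HF knowledge and HF caregiving self" and continues "efficacy scores by trial arm using paired t-tests for normally distributed data or Wilcoxon signed rank test for non-parametric data". The next sentence adds a second analysis: "We will examine the effect of randomization on the change in scores, using mixed linear regression models". That model has time as a three-level factor (baseline, post-course, 90 day), study arm, "a study arm by timepoint interaction and subject-specific random intercept". The same analyses are then applied to the secondary outcomes. The words primary analyses appear once, to name intention-to-treat as the analysis set.

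**Timing.** Under Study Design, after consent "all HHAs will attend a virtual orientation session and virtual HF training course", with baseline survey and 1:1 randomisation before the course. Then "HHAs in both arms will take a short post-course questionnaire (to assess the two primary outcomes; knowledge and HF caregiving self-efficacy"). App training is described after that survey: "HHAs randomized to the intervention will receive a just-in-time course refresher as well as an app training session". Sample Selection/Data Sources lists three surveys, the last of them "lastly at 90 days after the completion of the training course". Table 1 gives the source of the primary outcomes only as baseline and follow-up questionnaires.

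**Power.** Power and Sample Size gives a 1-point (knowledge) and an 8-point (self-efficacy) change, 80% power, alpha 0.05, 15% attrition, 104 HHAs (52 per arm), and Bonferroni over two hypotheses. It names no test, SD or timepoint.

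**The concern.** A paired t-test or signed-rank test asks whether scores moved within a group. The trial's question is whether they moved more in one randomised arm than in the other. The two arms contain different people, so nothing is paired between them, and comparing by trial arm with these tests can only mean one before-after test per arm. Both arms take the course between baseline and follow-up, so improvement in both is expected even if the additions in the intervention arm do nothing. A significant paired result there would reflect the course. A result significant in one arm but not the other is easily misread as a treatment effect.

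The mixed model answers the right question, so a between-arm test is not missing. The difficulty is that each primary outcome has two analyses and two post-baseline timepoints, which can disagree, and the plan does not say which decides. The timepoint matters in particular because the survey that Study Design ties to the primary outcomes comes, in the order described, before the app training that separates the arms.

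**Working it through.** **1. The plan's own figure.** The attrition step reproduces: 44/(1 − 0.15) = 51.8, so 52 per arm and 104 in total. The 44 cannot be checked because no SD is given. If it came from a two-sample t comparison at one timepoint with 80% power, the implied knowledge SD is about 1.50 at two-sided alpha 0.025 and 1.66 at 0.05.

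**2. Assumptions (not in the documents).** Knowledge SD σ = 1.5; within-person correlation ρ = 0.3, 0.5, 0.7; shared course gain of 1 or 0.5 point; n = 44 completers per arm; two-sided alpha 0.025 (Bonferroni over two outcomes, split equally).

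**3. Paired test when the intervention adds nothing.** SD of change = σ√(2(1 − ρ)). Noncentrality = gain × √44 / SD of change, on 43 df. For ρ = 0.5: SD of change = 1.5 × √1 = 1.5, and a 1-point gain gives 1 × 6.633/1.5 = 4.42.

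| ρ | SD of change | P(significant), gain 1 | P(significant), gain 0.5 | P(intervention arm only), gain 0.5 |
|---|---|---|---|---|
| 0.3 | 1.775 | 0.917 | 0.335 | 0.223 |
| 0.5 | 1.500 | 0.980 | 0.462 | 0.249 |
| 0.7 | 1.162 | 1.000 | 0.702 | 0.209 |

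The last column is p(1 − p), where p is the column before it, since the arms are independent. With alpha 0.05 and SD 1.65 instead, the values are 0.913, 0.976, 0.999 (gain 1); 0.383, 0.502, 0.718 (gain 0.5); and 0.236, 0.250, 0.203 (intervention arm only).

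**4. Mixed-model contrast under the same null.** Simulation of 40,000 trials per setting: three waves, equal variances and correlations, random-intercept contrast in closed form for balanced data, alpha 0.025. The 90-day contrast rejects in 0.025 to 0.028 of trials and the post-course contrast in 0.025 to 0.027. A shared course gain cancels between arms.

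**5. Timepoint.** Same simulation, with an intervention effect of 1 point at 90 days and none at the post-course survey.

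| ρ | 90-day contrast significant | Post-course contrast significant |
|---|---|---|
| 0.3 | 0.651 | 0.024 |
| 0.5 | 0.809 | 0.027 |
| 0.7 | 0.963 | 0.027 |

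Cross-check with a two-sample t-test on 90-day change, 86 df: noncentrality = 1/(SD of change × √(2/44)) = 2.64, 3.13, 4.04, so power is 0.642, 0.799, 0.959, close to the simulated values.

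**6. Multiplicity if the timepoint stays open.** Bonferroni over two hypotheses covers two outcomes with one test each. Testing both timepoints for both outcomes at 0.025 gives 1 − 0.975⁴ = 0.096 if all four tests are independent. It is about 0.091 with correlation 0.5 between timepoints and independent outcomes (both assumed). The stated level is 0.05.

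**The case against.** The strongest reply is that the right analysis is already planned. The mixed model is the one tied to the effect of randomisation, listing the paired tests first does not rank them first, and their wording can be read as within-arm description. No rule declares success from the intervention-arm paired test alone, so the 92% to 100% figures are not operating characteristics of this plan. They also rest on an assumed gain and correlation and on an SD back-calculated from N.

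Much of this is fair. The figures show what happens if the paired tests are used for the purpose the sentence gives them, and should be read no further. But that sentence does assign them the intervention effect, so as written the assignment is wrong. If they are meant as description, the plan should say so. Bonferroni over two hypotheses implies one test per outcome without identifying it. Pilot status does not remove the point, because the plan powers and adjusts both primary outcomes.

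Three qualifications stand:
- Both arms receive a refresher through Care Connect, so the contrast measures the added app training, messaging and reminders, not app exposure as such.
- App training carries no date, so its place after the post-course survey rests on the order of the narrative.
- The survey schedule has other loose ends. Study Design puts a follow-up questionnaire after care of the first patient, and the privacy section counts four questionnaire timepoints where Sample Selection/Data Sources counts three.

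**Conclusion.** The concern holds. The paired tests cannot estimate the intervention effect that the plan asks of them. Neither the primary analysis nor the primary timepoint is named, and the same gap carries to the secondary outcomes. Because a valid between-arm model is already specified, this is a mislabelled analysis and an open choice, not an absent one, and it should be fixed.

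The text alone establishes the defect. Its size depends on the assumed SD, correlation, course gain and 44 completers per arm. Across the range tried, the qualitative result does not change: the paired test responds to the shared gain, the between-arm contrast holds its level, and a contrast taken before the intervention acts has essentially no power for a later effect. Nothing here shows that 104 is the wrong sample size.

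**What to change.** - Remove the paired t-test and signed-rank test as tests of intervention effect, and report within-arm changes as descriptive.
- For each primary outcome, name the mixed-model arm-by-timepoint contrast at one stated timepoint as the sole primary analysis, so that the two Bonferroni hypotheses are identified.
- The 90-day survey is the logical timepoint, since app training is described after the post-course survey. The investigators should confirm it and reconcile it with the Study Design statement about the post-course questionnaire, and with the differing survey counts.
- If a simple supporting test is wanted, use a two-sample t-test or Wilcoxon rank-sum test on change between arms at that timepoint.
- Apply the same rule to the secondary outcomes.

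The cost is wording plus one decision. No new data are needed and N does not change by itself. The investigators should know, however, that under the assumptions above the 90-day contrast has about 65% power if the within-person correlation is only 0.3. If any outcome data have already been examined by arm, the amendment should say so, because the choice of timepoint would then not be prespecified.

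### The mixed model lets the arms differ at baseline although baseline precedes randomisation; a shared baseline mean would cut the variance of the 90-day effect by about 13% to 32% (planned attrition, assumed within-aide correlation 0.7 to 0.3)

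*Combined protocol and SAP*

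**What the plan says.** Under Outcome analyses, the plan states the purpose of the model: "We will examine the effect of randomization on the change in scores, using mixed linear regression models". Its terms are "a fixed effects categorical variable for time point (baseline/post-course/90 day") and "an indicator for study arm (control/intervention), a study arm by timepoint interaction and subject-specific random intercept". Baseline is therefore one of the outcome time points, and the arm indicator is a free between-arm difference at that time point.

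Two other sections fix the timing of baseline. Study Design has: "Prior to the course, all HHAs will complete a baseline questionnaire (see attached survey document) and be randomized in a 1:1 ratio (T1"). Sample Selection/Data Sources places the first of the three surveys before allocation: "prior to randomization); second after receiving the HF training course; and lastly at 90 days after the completion of the training course".

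The only further adjustment is for aide characteristics that differ between arms at p<0.10. Power and Sample Size gives the size of the trial: "with 80% power, α at 0.05, and conservatively allowing for 15% attrition, we will need 104 HHAs (52 per arm"). Neither an SD nor a within-aide correlation is stated.

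**The concern.** Randomisation after the baseline survey means that both arms are drawn from one population at baseline, so their true baseline means are equal. A model with an arm main effect ignores this and estimates the difference from the data. With complete data its arm-by-90-day coefficient is then the plain difference in mean change. That estimate does use baseline, but it subtracts the chance baseline difference in full, where the data support subtracting only a fraction ρ of it (ρ being the within-aide correlation).

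Precision is what is at stake. About 88 aides are expected to give a 90-day score, and preliminary effect estimates on the primary outcomes are a stated goal of the pilot. The baseline scores are already being collected and could narrow the confidence intervals at no data cost. The p<0.10 rule does not supply this gain: it concerns aide characteristics, is triggered only by an observed imbalance, and does not impose a common baseline mean of the outcome.

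**Working it through.** **Inputs.** From Power and Sample Size: 52 aides per arm and 15% attrition. From Outcome analyses: three time points and a random intercept, which implies equal variances and one common correlation ρ (compound symmetry). Assumed, because the plan gives no value: ρ = 0.3, 0.5, 0.7. The outcome SD cancels from every variance ratio, so σ = 1 below, and ρ is treated as known.

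**The plan's own figure.** The attrition step is consistent: 44/0.85 = 51.8, rounded up to 52 per arm, and 52 × 0.85 = 44.2 expected at 90 days. The 44 itself cannot be rebuilt without an SD.

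**Complete data, n per arm.**
- Planned (difference in mean change): Var = 2 × 2(1−ρ)/n.
- Shared baseline mean, or baseline as covariate: Var = 2 × (1−ρ²)/n.
- Ratio = (1−ρ²)/[2(1−ρ)] = (1+ρ)/2.

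| ρ | Planned, n=44 | Shared, n=44 | Ratio | Completers per arm the planned contrast needs (44/ratio) |
|---|---|---|---|---|
| 0.3 | 0.0636 | 0.0414 | 0.65 | 68 |
| 0.5 | 0.0455 | 0.0341 | 0.75 | 59 |
| 0.7 | 0.0273 | 0.0232 | 0.85 | 52 |

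**With the planned attrition.** Take n = 52 per arm at baseline and post-course, and m = 44.2 at 90 days. Let R² = 2ρ²/(1+ρ), the share of 90-day variance explained by the two earlier scores. Generalised least squares gives:
- Planned: Var = 2{(1−R²)/m + (R² + 1 − 2ρ)/n}.
- Shared: Var = 2{(1−R²)/m + (R² − ρ²)/n}.
- The difference is 2(1−ρ)²/n, which is positive for every ρ below 1.

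Example at ρ = 0.5, where R² = 0.3333:
- Planned: 2{0.6667/44.2 + 0.3333/52} = 0.0430.
- Shared: 2{0.6667/44.2 + 0.0833/52} = 0.0334.

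| ρ | Planned | Shared | Less variance | Smaller SE |
|---|---|---|---|---|
| 0.3 | 0.0597 | 0.0408 | 32% | 17% |
| 0.5 | 0.0430 | 0.0334 | 22% | 12% |
| 0.7 | 0.0260 | 0.0225 | 13% | 7% |

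If the 15% are lost directly after baseline instead, the range is 31% to 13%, so the timing of dropout hardly matters. A 90-day model with baseline as covariate, completers only, has variances 0.0412, 0.0339 and 0.0231, close to the shared-mean model.

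**Bias check.** In 20,000 simulated trials with no effect and 44 per arm, both estimators averaged zero to within 0.003. The change contrast moved by −0.70, −0.50 and −0.31 per unit of chance baseline difference at ρ = 0.3, 0.5 and 0.7; the baseline-adjusted estimate moved by about 0. This is the same variance point seen another way.

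**Power.** Assume two-sided α of 0.025 per outcome (Bonferroni) and 44 per arm. The effect size that gives 80% power for a two-sample comparison is then 0.667 SD. What follows depends on which SD was used:

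| SD behind N=104 | Model | ρ=0.3 | ρ=0.5 | ρ=0.7 |
|---|---|---|---|---|
| Single time point | planned | 64% | 80% | 96% |
| Single time point | shared | 84% | 91% | 98% |
| Change score | planned | 80% | 80% | 80% |
| Change score | shared | 94% | 91% | 87% |

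**The case against.** The planned model is a standard and valid one, it matches its stated target of change in scores, and it is unbiased. On this view the point is a choice between two sound estimators in a pilot whose effect estimates are called preliminary. That is fair as a limit on the claim: nothing in the planned result would be wrong, and no power shortfall is proven. It does not remove the gain, which rests on an equality that randomisation guarantees.

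The size depends on an assumed ρ. With the planned attrition the reduction is 41% at ρ = 0.1 and about 4% at ρ = 0.9. The direction is secure; the 13% to 32% holds only for ρ between 0.7 and 0.3.

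It also depends on the contrast. If the model-based 90-day difference (arm plus interaction) were reported, the gain would be 8%, 22% and 46% at ρ = 0.3, 0.5 and 0.7, rising with ρ instead of falling. The plan's wording on change points to the interaction, and there is a gain under either reading.

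The plan names paired tests before the mixed model and ranks neither. Study Design ties the post-course questionnaire to the primary outcomes, so 90 days is not clearly the primary time point. This stands as a condition on the claim. At post-course, with all 52 per arm observed, the interaction gains (1−ρ)/2, or 35%, 25% and 15%.

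Finally, the document is dated 4/22/2025 and describes the model partly in the past tense, so analysis may have begun. That is not certain, and it affects only how the change should be labelled.

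**Conclusion.** The concern holds. The mixed model estimates a baseline arm difference that is zero by design, and so gives up precision on the effect it is meant to estimate. For the arm-by-90-day coefficient under 15% attrition, the variance is 32%, 22% or 13% higher than it need be when expressed as the reduction available at ρ = 0.3, 0.5 or 0.7; on the standard-error scale the reduction is 17%, 12% or 7%. These figures assume compound symmetry and those values of ρ. The loss is of efficiency, not validity, and a power below 80% is not shown. The change should be made because it costs almost nothing and the sample is small.

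**What to change.** Remove the arm main effect so that both arms share one baseline mean: fixed effects for time, arm by post-course and arm by 90 days. Use the same form for the secondary outcome scores. A 90-day model with the baseline score as covariate is a close alternative, but it drops aides without a 90-day score.

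Preferably, also replace the random intercept alone with an unstructured covariance over the three time points, so that the standard error does not rest on compound symmetry. This is a separate point from the shared mean. For illustration, assume correlations of 0.3 (baseline/post-course), 0.2 (baseline/90-day) and 0.6 (post-course/90-day). The planned contrast then has a true per-arm variance factor of 2(1−0.2) = 1.60, but the random-intercept model reports 1.27. The shared-mean model with a random intercept has 0.99 and reports 0.87; with an unstructured covariance it has 0.96.

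It would help to state which SD (single-time or change) and which ρ lie behind the 104, but the change does not depend on it.

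Cost: a small edit to the model code and the analysis text, with no extra data. If outcome data have already been analysed, keep the planned model as specified and report the shared-baseline model as a labelled sensitivity analysis.

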Outcomes	Validated Scale	Description	Data source
Primary Outcomes (HCWs)			
HF knowledge	Dutch HF Knowledge Scale	15 item scale measures HF knowledge in general, knowledge of HF treatments, and HF symptom recognition. Scores range from 0-15, with higher scores indicating higher HF knowledge.	Baseline and follow-up questionnaires
HF caregiving self-efficacy	Caregiver Contribution to Self-Care in HF Index (CC-SCHFI)	22-item scale measures caregivers' 1) contributions to HF maintenance; 2) contributions to HF management; and 3) HF caregiving self-efficacy (confidence). Each of these 3 subscales are scored independently. The third sub-scale (self-efficacy) will be the main outcome. Self-efficacy scores range from 0-100, with higher scores indicating greater self-efficacy.	Baseline and follow-up questionnaires
Secondary Outcomes (HCWs)			
Intention to Leave	Turnover intention scale	2-item scale measures workers' intentions of 1) leaving their current job (at their agency) and 2) searching for a new job (in another field) in the next year	Baseline and follow-up questionnaires
Job satisfaction	Work Domain Satisfaction Scale	This 5-item scale measures 1) job satisfaction among care workers; and 2) examines the associations with work environment factors, work stressors, and health issues. Scores range from 5-20, with higher scores indicating stronger satisfaction.	Baseline and follow-up questionnaires
Other Specified Outcomes			
Communication practices	Preventable 911 Calls	2 novel questions “I have called 911 when that could have been prevented if I had been able to reach my supervisor/the nurse.” And “I have called 911 when that could have been prevented if my supervisor and I had been able to reach the client's doctor.”	Baseline and follow-up questionnaires

		Responses for both included a 7-point likert scale of: very strongly disagree, strongly disagree, disagree neutral, agree, strongly agree, very strongly agree. Both questions dichotomized into “agree”, “strongly agree”, and “very strongly” vs. all other responses.	
Patient Outcomes (exploratory)			
30-day readmission; 90-day (all-cause)	N/A	A readmission to any hospital (for any reason) at 30-days after start of home care episode.	Follow-Up VNS Health administrative data
Emergency department visit (all-cause)	N/A	A visit to the emergency department of any hospital (for any reason) after start of home care episode	Follow-Up VNS Health administrative data

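### With only a random intercept over three surveys, the model-based standard error of a single arm-by-time contrast on the primary scores can be wrong in either direction

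*Combined protocol and SAP*

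**What the plan says.** All references are to the combined protocol and SAP.

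- **Model.** Under Brief Overview of Analytic Methods, Outcome analyses, the plan states: "We will examine the effect of randomization on the change in scores, using mixed linear regression models". The fixed effects are a three-level time factor, arm and their interaction. The covariance is described only in "a study arm by timepoint interaction and subject-specific random intercept". No random slope, other residual structure, robust standard error or covariance sensitivity analysis is mentioned.
- **Other tests.** The primary scores are also to be compared "using paired t-tests for normally distributed data or Wilcoxon signed rank test for non-parametric data". As named, these are within-person tests, so the mixed model is the only between-arm analysis of change that is described.
- **Timing.** The first survey precedes orientation and the course. Study Design adds: "After taking the course, HHAs in both arms will take a short post-course questionnaire". Sample Selection/Data Sources places the second survey "second after receiving the HF training course" and the third "lastly at 90 days after the completion of the training course".
- **Scales.** For knowledge, Table 1 states: "Scores range from 0-15, with higher scores indicating higher HF knowledge". Self-efficacy runs from 0 to 100.
- **Error control.** Power and Sample Size sets an overall alpha of 0.05 with Bonferroni over two hypotheses, which is 0.025 each if applied.

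**The concern.** A random intercept with independent residuals is compound symmetry: one variance at every survey and one correlation for every pair of surveys. The fitted model therefore gives every change contrast the same variance, pooled over all three pairs.

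Three design features make equality doubtful. The course falls between surveys 1 and 2 in both arms, while surveys 2 and 3 are both after training. The gap from post-course to the last survey is 90 days, whereas the gap from baseline to post-course is short but not stated. Both scales are bounded, so the spread may change if training moves scores toward a limit.

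If baseline and 90 days are the least correlated pair, the model-based standard error for that change is too small and the test rejects too often. If they are the most correlated pair, the test is conservative. The stake is whether the intervals and p-values for the between-arm change in the two primary scores mean what the stated alpha says. These estimates would also inform any larger trial.

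**Working it through.** **Inputs.** From the documents: three time points, 1:1 allocation, 52 HHAs per arm, 15% attrition. This leaves 52 × 0.85 ≈ 44 per arm, or 88 in all. Assumed, because the documents give none: SDs and correlations. Correlations are listed as baseline/post-course, baseline/90-day, post-course/90-day. The plan gives no figure for the precision of the contrast, so there is none to reproduce.

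**Formulas (complete data).** Let s_jk be the true covariance of surveys j and k.

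- True variance of a change: V_jk = s_jj + s_kk − 2 s_jk.
- Variance of a change under the fitted random intercept, for every pair: V_model = 2 × (mean variance − mean covariance), which equals the mean of the three V_jk.
- Ratio of model SE to true SE: r = √(V_model / V_jk). The number per arm cancels.
- Actual size of a two-sided test with critical value z: 2Φ(−z r).

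**Worked pattern 0.5/0.4/0.7, unit SDs.**

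- Baseline to post-course: 2 − 1.0 = 1.0. Baseline to 90 days: 2 − 0.8 = 1.2. Post-course to 90 days: 2 − 1.4 = 0.6.
- V_model = (1.0 + 1.2 + 0.6)/3 = 0.933.
- Baseline to 90 days: r = √(0.933/1.2) = 0.882. Size at 5%: 2Φ(−1.960 × 0.882) = 8.4%. Size at 2.5%: 2Φ(−2.241 × 0.882) = 4.8%.
- Baseline to post-course: r = √(0.933/1.0) = 0.966, size 5.8%.
- Post-course to 90 days: r = √(0.933/0.6) = 1.247, size 1.5%.
- Joint two-degree-of-freedom interaction: the model gives each of two orthonormal within-person contrasts a variance of 0.933/2 = 0.467. Their true covariance matrix has eigenvalues 0.643 and 0.290, ratios 1.378 and 0.622. The statistic is then distributed as 1.378 χ²₁ + 0.622 χ²₁, which exceeds the 5% critical value of χ²₂ about 5.5% of the time.

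**Other patterns, baseline to 90 days, nominal 5%.** The last two columns are simulated: 52 per arm, 15% missing at random at 90 days, REML random-intercept fit, 4,000 runs.

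| Correlations (SDs equal unless stated) | r | Closed form | Simulated, model SE | Simulated, cluster-robust SE |
|---|---|---|---|---|
| 0.5/0.5/0.5 | 1.00 | 5.0% | 5.3% | 5.7% |
| 0.6/0.5/0.55 | 0.95 | 6.3% | 7.0% | 5.5% |
| 0.5/0.5/0.5, SDs 1, 0.7, 0.8 | 0.93 | 6.7% | 6.4% | 5.2% |
| 0.4/0.4/0.7 | 0.91 | 7.4% | 6.2% | 5.0% |
| 0.8/0.4/0.45 | 0.87 | 9.0% | 9.4% | 5.0% |
| 0.7/0.49/0.7 | 0.85 | 9.5% | 10.3% | 5.8% |
| 0.7/0.4/0.6 | 0.85 | 9.6% | 10.5% | 6.1% |
| 0.4/0.6/0.4 (reverse) | 1.15 | 2.4% | 2.3% | 5.0% |

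Further mild patterns in closed form: 0.5/0.5/0.6 gives 5.8%, 0.6/0.6/0.7 gives 6.1%, 0.55/0.5/0.6 gives 6.3% and 0.5/0.5/0.7 gives 6.8%.

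The worked pattern was also simulated. With 44 complete per arm (20,000 runs) the random-intercept test ran at 8.3%, and a test using the change-score variance from the two surveys concerned ran at 5.1%. With 52 per arm and 15% missing (3,000 runs) the random-intercept test ran at 7.9%.

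**The case against.** The strongest reply is that the departure is inferred from the design rather than shown. No SD, correlation or baseline mean appears in the documents. A fall in variance after the course needs scores to move close to a limit, and nothing says they will; a course that helps some HHAs more than others could widen the spread. Mild patterns that fit the same design reasoning cost only one or two percentage points. This stands, and it is why the result is a range that includes conservative cases.

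Second, the plan does not name baseline to 90 days as the primary contrast and does not label the mixed model as the primary analysis. Study Design in fact ties the post-course questionnaire to the two primary outcomes. If the joint interaction test were used, the effect would be small. This also stands. The 90-day contrast remains a natural one, because app training and use follow the course, and no other between-arm analysis of change is described.

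Third, a random intercept is a common choice for three visits, the trial is a pilot, and with complete data the point estimate is unaffected. That is true, but it limits the consequence without favouring compound symmetry. With attrition, the assumed covariance also affects how incomplete records are weighted.

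A reader might infer that the trial's real type I error is 8.4%, or that the test must be too liberal. The documents support neither. The 8.4% belongs to one assumed pattern and one contrast, and the error can go the other way.

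**Conclusion.** The point holds as a conditional one. The plan fixes compound symmetry for its only described between-arm analysis of change, and the design gives reasons to doubt it. For a single contrast, baseline to 90 days, the assumed patterns move a nominal 5% test from about 2.4% to about 10%, with exactly 5% in large samples when variances and correlations are equal. In the worked pattern a 2.5% Bonferroni test runs at 4.8%, which would use up most of the protection that the adjustment is meant to give. These figures rest on assumed correlations and SDs, independent residuals, and a single-contrast test using model-based standard errors. It is a worthwhile improvement to the specification. It does not show that the planned analysis is invalid.

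**What to change.** Keep the fixed effects (time, arm, arm by time). Replace the random intercept with an unstructured residual covariance over the three surveys: in Stata, `mixed` with no random intercept, `residuals(unstructured, t(time))`, REML and Kenward-Roger degrees of freedom. If this does not converge, use the random-intercept model with standard errors clustered by HHA. The fallback should not be the random intercept with model-based errors, since that restores the problem. State which arm-by-time contrast or joint test carries the between-arm conclusion, because the size of the effect depends on it.

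The cost is a sentence or two in the analysis section and six covariance parameters instead of two, which is small with about 88 to 104 HHAs. The sample size of 104 and the data collection do not change. The simulations above checked robust errors (5.0% to 6.1%) and a two-survey change-score variance (5.1%), not the unstructured fit itself. If the planned model has already been fitted, report both analyses and mark the unstructured one as added afterwards.
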